#### **10.4.2 Primary Safety Endpoint**

The primary safety endpoint is the incidence of any primary adverse event (PAE) occurring within 7 days of the AF ablation procedure (including the initial and repeat procedures) using the

study catheter per protocol. The primary safety rate of the investigational device will be compared to a pre-determined performance goal of 16%.

The primary safety endpoint will be evaluated using the two-sided 95% exact confidence interval for the primary safety rate. If the upper bound of the exact confidence interval of the primary safety rate is less than the performance goal of 16%, the study will be considered to have demonstrated safety.

The safety population (SP) will be used as the primary analysis population. Subjects with missing primary safety data will be excluded in the primary analysis. Sensitivity analyses for missing data will be performed using the SP and are outlined in section 10.4.3.

### **10.4.3 Handling of Missing Data**

#### **10.4.3.1 Primary Effectiveness Endpoint**

Several sensitivity analyses will be performed to assess the robustness of results with regard to missing data for the primary effectiveness outcome. All analyses will be performed in the PP and mITT populations, which include but are not limited to the following:

##### *1) Best-Case Scenario*

Subjects with missing effectiveness outcome will be treated as effectiveness success. The point estimate for freedom from recurrence of atrial tachyarrhythmias and the exact two-sided 95% confidence interval will be presented.

##### *2) Worst-Case Scenario*

Subjects with missing effectiveness outcome will be treated as effectiveness failure. The point estimate for freedom from recurrence of atrial tachyarrhythmias and the exact two-sided 95% confidence interval will be presented.

##### *3) Multiple Imputation*

Multiple imputations will be used to impute missing data for the effectiveness outcome. A multivariate logistic regression model incorporating the demographic and baseline characteristics will be used to impute missing values for the primary effectiveness outcome. Five imputed datasets will be generated. The imputed datasets will then be combined to incorporate both within- and between imputation variability.

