7.2 Analyses for Primary Endpoints

7.2.1 Analyses for Primary Effectiveness Endpoint

The null and alternative hypotheses are:

Hypothesis $H_0: P_E \leq 0.40$

$H_a: P_E > 0.40$

P_E : the freedom from documented atrial fibrillation, atrial flutter and atrial tachycardia recurrence at 15 months follow-up

Null hypothesis: The freedom from documented AF/AFL/AT at 15 months is less than or equal to the pre-determined performance goal of 40%.

Alternative hypothesis: The freedom from documented AF/ATL/AT at 15 months is greater than the pre-determined performance goal of 40%.

Analysis Population: The per-protocol population will be used as the primary analysis population. Subjects with missing effectiveness endpoints data during 15 months follow-up period will be excluded from the primary analysis. The subjects who have failed the primary effectiveness endpoint before 15 months will be included in the analysis. Analyses of the primary effectiveness endpoint will be repeated in the mITT population. Sensitivity analyses for missing data will be performed in the PP and mITT populations to assess the impact of missingness on the primary effectiveness outcome and are described in the Statistical Analysis Plan (SAP).

Analysis Method: The primary effectiveness endpoint will be evaluated using the exact test for a binomial proportion at a two-sided significance level of 5%. If the lower bound of the exact two-sided 95% confidence interval of the primary effectiveness endpoint rate is greater than the performance goal of 40%, the study will be considered to have demonstrated effectiveness.

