## **9 Sample Size Justification**

### **9.1 Primary Effectiveness Endpoint**

The primary effectiveness endpoint is freedom from documented atrial tachyarrhythmia recurrence without failure modes during the evaluation period (Day 181-450). A performance goal of 40% is set for the primary effectiveness endpoint. Please refer to Section 4.1 of the protocol for justifications of performance goals for the primary effectiveness endpoint.

Based on a performance goal of 40% and an anticipated freedom from AF recurrence rate of 50%, 330 subjects will be required to obtain at least 90% power at a two-sided significance level of 0.05 using the exact binomial method.

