### **9.3 Total Sample Size**

It is estimated that the attrition rate is no more than 10%. In order to obtain 330 subjects, Biosense Webster proposes to enroll 367 ( $=330/0.90$ ) subjects to account for this potential subject attrition.

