### **10.4 Primary Endpoints Analyses**

#### **10.4.1 Primary Effectiveness Endpoint**

The primary effectiveness endpoint is defined as achieving effectiveness success at 12 months after undergoing an RF ablation procedure using the THERMOCOOL® SMARTTOUCH™ SF catheter. The primary effectiveness rate will be compared to a pre-determined performance goal of 40%.

The primary effectiveness endpoint will be evaluated by constructing the two-sided 95% exact confidence interval for the effectiveness rate. If the lower bound of the exact confidence interval of the primary effectiveness endpoint rate is greater than the performance goal of 40%, the study will be considered to have demonstrated effectiveness of the device.

The per protocol population (PP) will be used as the primary analysis population for effectiveness. Subjects with missing effectiveness data during the 15-month follow-up period will be excluded from the primary analysis.

Analyses of the primary effectiveness endpoint will be repeated using the mITT population. Subjects with catheter inserted but no RF delivered due to investigational device deficiency in the mITT population will be categorized as effectiveness failures and included in the analysis. Subjects with no RF delivery due to other reasons (e.g. anatomical difficulty, complications) will be excluded from the mITT analysis and be included in the sensitivity analysis for missing data.

Sensitivity analyses for missing data will be performed using the PP and mITT populations to assess the impact of missingness on the primary effectiveness outcome and are outlined in section 10.4.3.

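### The multiple imputation in SAP 10.4.3.1 ignores observed failure-free time, so it nearly returns the complete-case rate and is weak evidence about missing data

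*SAP*

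**What the plan says.** **Who is missing.** SAP 10.4.1 states: "Subjects with missing effectiveness data during the 15-month follow-up period will be excluded from the primary analysis". Protocol 7.2.1 makes the same exclusion but adds: "The subjects who have failed the primary effectiveness endpoint before 15 months will be included in the analysis". A subject with a known failure is therefore always counted, whatever happens later.

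**How item 3 fills the gap.** In SAP 10.4.3.1, item 3: "A multivariate logistic regression model incorporating the demographic and baseline characteristics will be used to impute missing values for the primary effectiveness outcome". The next sentence is: "Five imputed datasets will be generated". The SAP does not say that baseline variables are the only predictors, but it lists no others.

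**What else is planned.** The same section has best-case, worst-case and tipping-point analyses. SAP 10.4.5.2 adds an exploratory Kaplan-Meier analysis of AF/AT/AFL recurrence in the PP and mITT populations.

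**What is collected.** Protocol 5.15 schedules monthly TTM transmissions at months 7 to 15 and Holter recordings at months 6, 12 and 15, so failure-free time during the evaluation period is observed.

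**The concern.** In the PP population, every subject with a missing outcome had no recorded failure when last seen. The complete cases keep all early failures and lose some subjects who were still failure-free. They therefore hold too many failures, and the imputation model is fitted to them.

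With equal baseline covariates, a subject failure-free to month 14 and one lost at month 1 get the same probability of success, although the first has already passed through most of the evaluation period. Item 3 is the only model-based missing-data analysis of the primary composite itself. If its result agrees with the complete-case result, a reader will take that as reassurance, when the method makes the agreement likely in any event.

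**Working it through.** **Inputs from the documents.** Goal 40% and anticipated rate 50% (SAP 9.1); attrition of at most 10% and enrolment of 367 (SAP 9.3); evaluation period Day 181-450 (SAP 6.1.1); five imputations.

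**Assumed, because the documents give no figures.** Failure times and dropout times, and dropout unrelated to outcome unless stated.

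**The plan's own figures.** 330/0.90 = 366.7, so 367 reproduces. SAP 9.1 claims "at least 90% power at a two-sided significance level of 0.05 using the exact binomial method". With the exact rule at n = 330, success needs at least 151 of 330; one-sided alpha is 0.0193 and power at 50% is 94.5%. The claim holds.

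**Probability of success given failure-free time.** With a constant hazard over Day 181-450 and 50% success overall, P(success | failure-free at day d) = 0.5^((450-d)/270).
- Day 270: 0.5^(180/270) = 63%
- Day 360: 0.5^(90/270) = 79%
- Day 420: 0.5^(30/270) = 93%

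Item 3 gives each of them about 49%, as shown next.

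**Success among missing subjects.** Let S = 0.5, d = 0.10, and q = the chance that a subject who drops out and would fail leaves before failing. With dropout uniform over Day 0-450, q = (mean failure day)/450.
- Missing fraction: m = d[S + (1-S)q]
- True success among the missing: dS/m
- Complete-case rate: CC = S(1-d)/[S(1-d) + (1-S)(1-dq)]

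*Uniform failures:* mean day 315.5, q = 0.701.
- m = 0.1(0.5 + 0.3506) = 0.0851
- true success among the missing = 0.05/0.0851 = 58.8%
- CC = 0.45/(0.45 + 0.4649) = 49.2%, a bias of -0.8 point

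*Constant hazard:* mean day 180 + 270(1/ln 2 - 1) = 299.5, q = 0.666.
- m = 0.1(0.5 + 0.333) = 0.0833
- true success among the missing = 0.05/0.0833 = 60.0%
- CC = 0.45/(0.45 + 0.4667) = 49.1%, a bias of -0.9 point

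If the imputation uses only variables unrelated to dropout, each missing subject succeeds with probability CC. The overall rate is then (1-m)CC + m·CC = CC, which is the complete-case rate again.

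**Range over timing.** Six combinations were tried at 10% dropout: failures uniform, uniform with 10% acute at Day 0, or early (exponential, mean 60 days), each with dropout uniform over Day 0-450 or Day 181-450. The bias runs from -0.8 to -2.1 points. The bound, with every failure before any dropout, is 0.45/0.95 = 47.4%, or -2.6. At 20% dropout the range is -1.8 to -4.4.

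**Fitting the imputation itself.** 600 simulated trials of 367; 10% of failures acute at Day 0; dropout uniform over Day 1-450; three baseline covariates, two of them prognostic. Mean success rates in percent (simulation error about 2.7/√600 = 0.1 point):

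| Dropout; failure timing; dropout related to baseline? | Truth | Complete cases | Item 3 | Imputed given failure-free time | Kaplan-Meier |
|---|---|---|---|---|---|
| 10%; uniform; no | 49.99 | 49.06 | 49.10 | 50.05 | 50.04 |
| 10%; early; no | 49.86 | 48.45 | 48.53 | 49.86 | 49.85 |
| 10%; uniform; yes | 49.81 | 48.30 | 48.77 | 49.44 | 49.45 |
| 10%; early; yes | 50.03 | 48.13 | 48.56 | 49.73 | 49.74 |
| 20%; uniform; no | 50.04 | 47.91 | 48.03 | 50.12 | 50.10 |
| 20%; early; no | 49.99 | 47.00 | 47.21 | 50.03 | 50.02 |

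Item 3 recovers at most 0.2 point when dropout is unrelated to baseline. At 10% dropout it recovers 0.4 to 0.5 point when dropout depends on a prognostic covariate.

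**Direction.** At a true rate of 40%, with 10% dropout and uniform timing, CC = 0.36/(0.36 + 0.5579) = 39.2%. The one-sided type I error of the exact complete-case test is then about 0.009. At a true 50%, its power is 0.83 to 0.92 over the six timings, with 367 treated.

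**Five imputations.** With 31 missing of 367, the between-imputation variance is about 31×0.25/367² + (31/367)²×0.25/336 = 6.3×10⁻⁵. The Monte Carlo error is √(6.3×10⁻⁵/5) = 0.35 point with 5 imputations and 0.11 with 50. The sampling error is √(0.25/367) = 2.6 points.

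**The case against.** **A reader might infer that item 3 would falsely suggest robustness.** The documents do not support this. With non-informative dropout the error runs against the device, so a pass on the imputed data would on average also be a pass on better-imputed data. This objection stands.

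**The unfavourable direction is already covered.** Worst case and tipping point span every possible completion of the missing data. This stands for bounding the result. But neither uses failure-free time, so neither shows where in that span the missing outcomes plausibly lie.

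**Failure-free time is already used.** The Kaplan-Meier analysis in SAP 10.4.5.2 accounts for censoring and recovers the truth in four of the six simulated cases, the exceptions being those with baseline-related dropout. This stands in part. The analysis is exploratory, covers recurrence rather than the full composite of failure modes in SAP 6.1.1, and is not compared with 40%. The Kaplan-Meier analysis in SAP 10.6.2 is likewise for recurrence.

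**The premise is not universal.** A reader might infer that every missing subject was failure-free in follow-up. SAP 10.4.1 also sends to this analysis the mITT subjects who had no RF delivered for reasons other than device deficiency. They were never ablated, and SAP 10.2 follows them for 30 days. The argument therefore applies to ablated subjects only.

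**Many leavers add no information.** With dropout uniform over Day 0-450, 0.04/0.0833 = 48% of missing subjects leave before Day 181, before any evaluation-period failure-free time exists. For them 49% is close to the assumed 50%, and the gain comes from the rest.

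**Five imputations.** The Monte Carlo error is small beside the sampling error. Raising the number is a free gain, not a correction of a serious fault.

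**Conclusion.** The point holds as a minor one. In the PP population, item 3 as written approximately returns the complete-case rate, so agreement between the two is not independent evidence about missingness. It is approximate because the model does adjust for baseline differences.

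Under the planned 50% success and 10% attrition, the bias is about -1 point, and -0.8 to -2.1 over the timings tried. It costs power and does not create a false success. These figures rest on assumed failure and dropout timing and on non-informative dropout.

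If leavers have more unrecorded recurrences than those who stay, the bias could reverse. Item 3 would still follow the complete cases, and so would an imputation based on failure-free time. Only the worst-case and tipping-point analyses would show that problem.

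**What to change.** Rewrite SAP 10.4.3.1 item 3 as follows:
- Impute time to first failure of the full primary composite, for example with a discrete-time hazard model using the same baseline covariates.
- Condition on being failure-free at the last rhythm recording in the evaluation period. Impute subjects lost before Day 181 from the start of that period.
- Derive Day-450 success from the imputed times.
- Use more imputations, for example 50.
- State a separate rule for mITT subjects with no RF delivered, since conditioning on failure-free follow-up does not apply to them.
- Keep the worst-case and tipping-point analyses for informative dropout.

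The cost is SAP wording and modest extra programming. No new data are needed, since the rhythm recordings are already scheduled, and the primary analysis does not change.

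### With five imputations and 10% of outcomes missing, the multiple-imputation lower limit would carry about ±0.9 points of random-seed noise, which matters only if observed success is near 45–46%

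*SAP*

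**What the plan says.** SAP 10.4.1 bases the effectiveness decision on the exact two-sided 95% interval in the per-protocol population, compared with a goal of 40%. Missing outcomes do not enter it: "Subjects with missing effectiveness data during the 15-month follow-up period will be excluded from the primary analysis".

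SAP 10.4.3.1 then lists supporting analyses, in the per-protocol and mITT populations: "Several sensitivity analyses will be performed to assess the robustness of results with regard to missing data for the primary effectiveness outcome". They are a best case, a worst case, multiple imputation, a tipping-point analysis and some descriptive comparisons.

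For multiple imputation the text is short. The model: "A multivariate logistic regression model incorporating the demographic and baseline characteristics will be used to impute missing values for the primary effectiveness outcome". The number: "Five imputed datasets will be generated". The combination: "The imputed datasets will then be combined to incorporate both within- and between imputation variability". The SAP gives no seed, no reason for five, no criterion for Monte Carlo error and no pass/fail rule for this analysis.

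SAP 9.1 sizes the trial for a 50% success rate against 40%: "330 subjects will be required to obtain at least 90% power at a two-sided significance level of 0.05 using the exact binomial method". SAP 9.3 allows for attrition of no more than 10%, giving 367 enrolled.

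**The concern.** Multiple imputation draws the missing outcomes at random, so its estimate and interval depend on the seed. The dependence shrinks as the number of imputations grows. With five it may be visible at the precision to which the limit would be reported.

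The analysis has a real job here. With 37 outcomes missing, the best and worst cases lie far apart: the exact rule needs 151/330 for primary success, but 166/367 when all missing subjects count as failures. From 151 to 165 observed successes the primary test and the best case pass while the worst case fails. That includes the planned 50%, since 165/367 has an exact lower limit of 39.8%. Within SAP 10.4.3.1, multiple imputation is the only analysis that gives a modelled estimate between those bounds. If its lower limit sat close to 40%, a reader might take a seed effect for evidence about the missing data. With no seed stated in advance, a favourable rerun could not be ruled out either.

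**Working it through.** **1. The plan's own figures.** Attrition: 330/0.90 = 366.7, so 367 (SAP 9.3) reproduces. Exact lower 95% limits: 150/330 gives 39.99% and 151/330 gives 40.29%, so 151 (45.8%) is the smallest passing count. P(X ≥ 151 | 330, 0.40) = 0.0193 and P(X ≥ 151 | 330, 0.50) = 94.5%. The statement of at least 90% power is correct.

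**2. Inputs for the noise calculation.**
- From the SAP: M = 5 imputations (10.4.3.1), goal 40% (10.4.1), anticipated rate 50% and 330 evaluable (9.1).
- Assumed: 330 observed plus 37 missing, outcomes missing at random, an intercept-only imputation model with a posterior draw of the rate, and Rubin's rules with t degrees of freedom. The SAP names neither the rule nor the reference distribution.

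**3. Approximate size by formula.** With n_obs = 330, m = 37, n = 367 and p = 151/330, the between-imputation variance is about

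B = (m/n)² · p(1−p) · (1/n_obs + 1/m), so √B = 0.87 points.

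The seed-to-seed SD of the combined estimate is √(B/M): 0.87/√5 = 0.39 points for M = 5, and 0.87/√50 = 0.12 for M = 50.

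The lower limit is L = Q − t·√T, with Q the combined estimate and T = W + (1 + 1/M)B, where W is the within-imputation variance. B is itself estimated from M values, so the width of the interval varies too and L is noisier than Q.

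**4. Simulation.** The observed data are held fixed and only the seed varies. Noise is 1.96 × SD(L), at 10% missing.

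| M | SD(L), points | Noise, points |
|---|---|---|
| 5 | 0.46 | ±0.90 |
| 20 | 0.21 | ±0.42 |
| 50 | 0.13 | ±0.26 |

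Variations with M = 5:
- 5% missing: ±0.57 to ±0.61.
- 15% missing: about ±1.2.
- 297 observed plus 33 missing: ±0.93 to ±0.96.
- 6 to 10 simulated covariates in the model: ±0.76 to ±0.93.

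**5. When the noise can cross 40%** (330 observed plus 37 missing).

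| Observed successes | Rate | M = 5 runs below 40% | M = 50 runs below 40% |
|---|---|---|---|
| 151 | 45.8% | 24% | 0.2% |
| 152 | 46.1% | 10% | 0% |
| 153 | 46.4% | 3% | 0% |
| 155 | 47.0% | 0.2% | 0% |
| 165 | 50.0% | none | none |

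At 165/330 the M = 5 limit ranges from 43.6% to 45.4%. Between 2.5% and 97.5% of M = 5 runs exceed 40% only for 148 to 153 successes (44.8% to 46.4%). At 148 to 150 the primary test has already failed.

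**6. How likely that is.** The chance of observing 148 to 153 of 330 is 7.6% if the true rate is 50%, and about 25% if it is 45–46%. The chance that the primary test passes and an M = 5 run still falls below 40% is the sum over x ≥ 151 of P(X = x) times the share of runs below 40%. This is about 0.5% at a true rate of 50% and about 1.6% at 45–46%.

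**The case against.** A reader might infer that seed noise puts the 40% conclusion in doubt generally. The documents do not support that, for four reasons, all of which stand.

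- The success claim rests on the exact interval without missing subjects. Multiple imputation is one supporting analysis, with no decision rule attached.
- The best-case, worst-case and tipping-point analyses use no seed. The tipping-point analysis is to cover every possible split of the missing outcomes, so a result close to the goal would show there whatever the imputation run gave.
- The 10% is a ceiling on attrition from enrolment, and enrolment means signed consent (Protocol 3.0 and 3.2). It can include people who never had the catheter inserted, who are in neither the per-protocol nor the mITT set. Subjects who fail before leaving are not missing (Protocol 7.2.1). The missing share in the analysed sets may well be smaller.
- Away from an observed rate of about 45–46%, the limit does not straddle 40%.

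It can also be said that five is not a mistake. Rubin's rules inflate the variance by (1 + 1/M) and use t degrees of freedom, so the interval allows for few imputations, and an SD of 0.46 points is small beside a standard error of about 2.8. That is fair as to validity. It does not make a single run reproducible to the precision at which a limit near 40% would be read, and the remedy costs nothing.

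**Conclusion.** Five imputations leave avoidable noise in one sensitivity analysis: about ±0.9 points in the lower limit if 10% of outcomes are missing, and about ±0.6 at 5%. With 50 imputations and 10% missing it would be about ±0.26. It could change the reading of that analysis only for an observed rate of about 45–46%; at 151/330, 24% of M = 5 runs would fall below 40%, against 0.2% with M = 50. It would not do so at the planned 50%, and it does not touch the primary test. The figures assume data missing at random, Rubin's rules with t intervals, and simulated covariates where any are used, because the documents give no covariate effects. This is a minor improvement, worth making because it is free.

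**What to change.** In SAP 10.4.3.1 item 3, replace five with a larger number, such as at least 50. The documents do not dictate that figure: 20 would already bring the noise to about ±0.42 points, and 50 brings it to about ±0.26. State the random seed in the SAP before database lock. The seed makes the run reproducible and removes any question of reruns, but does not by itself reduce the noise. The cost is one sentence and negligible computing time, with no effect on subjects, endpoints, sample size or the primary test.

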##### *4) Tipping Point Analysis*

In this study, the tipping point is defined as the number of subjects with recurrent atrial tachyarrhythmia at which the study conclusion is changed. The tipping-point analysis will replace the missing values with effectiveness failures one at a time and the corresponding Z test statistic will be produced. If the Z value is equal to or less than  $Z_{1-\alpha/2}$ , the resulting number of imputed failures is the tipping point. The significance level will be set at  $\alpha=0.05$ .

The tipping-point analysis for the effectiveness endpoint will analyze all possible cases that may occur in the missing data cohort. The results will be presented in a summary table to illustrate how p-value and conclusion on meeting the performance goal changes. As listed below, additional analyses may also be performed to assist clinical judgment on whether such a tipping point is implausibly unfavorable.

5) *Additional analyses:*

- The demographic and baseline characteristics will be compared between cohorts with and without missing data for the primary effectiveness endpoint.
- The reasons for missingness, if available, will be listed for missing data by site.

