#### **10.4.3.2 Primary Safety Endpoint**

The following sensitivity analyses will be performed in the SP.

1) *Best-Case Scenario*

Subjects with missing safety outcome will be treated as free from primary adverse events. The point estimate for freedom from early onset primary adverse events and the corresponding exact two-sided 95% confidence interval will be presented.

2) *Worst-Case Scenario*

Subjects with missing safety outcome will be treated as having experienced a primary adverse event. The point estimate for freedom from early onset primary adverse events and the corresponding exact two-sided 95% confidence interval will be presented.

3) *Tipping Point Analysis*

In this study, the tipping point is defined as the number of subjects with primary AEs for the binary safety endpoint in the study population at which the study conclusion is changed. The tipping-point analysis will replace the missing values with primary AE occurrence one at a time and the corresponding Z test statistic will be produced. If the Z value is equal to or greater than  $Z_{\alpha/2}$ , the resulting imputed number of primary AE is the tipping point. The significance level will be set at 0.05.

The tipping-point analysis for binary safety endpoints will analyze all possible cases that may occur in the missing data cohort. The results will be presented in a summary table to illustrate how Z statistic and conclusion on meeting performance goal changes. As listed below, additional analyses may also be performed to assist clinical judgment on whether such a tipping point is implausibly unfavorable.

4) *Additional analyses:*

- The demographic and baseline characteristics will be compared between the observed data cohort and missing data cohort. Fisher' exact test will be used for binary variables and Krustal-Wallis test will be used for continuous outcomes as appropriate.
- The reasons for missingness, if available, will be listed for missing data by site.

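### SAP 10.4.3 finds the tipping points with a Z test of unstated form, although the exact 95% confidence interval decides the study and the worst case

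*SAP*

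**What the plan says.** **The decision rules are exact.** Protocol 7.2.1 states: "The primary effectiveness endpoint will be evaluated using the exact test for a binomial proportion at a two-sided significance level of 5" per cent. SAP 10.4.1 turns this into an interval rule: "If the lower bound of the exact confidence interval of the primary effectiveness endpoint rate is greater than the performance goal of 40" per cent, effectiveness is shown. SAP 10.4.2 does the same for safety: "If the upper bound of the exact confidence interval of the primary safety rate is less than the performance goal of 16" per cent, safety is shown. Protocol 7.2.2 matches it.

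**The worst case is exact.** In SAP 10.4.3.1 all missing subjects are scored as failures, and "The point estimate for freedom from recurrence of atrial tachyarrhythmias and the exact two-sided 95% confidence interval will be presented". The safety worst case in SAP 10.4.3.2 is also reported with an exact interval.

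**The tipping point is defined by the study conclusion.** SAP 10.4.3.1 says that "the tipping point is defined as the number of subjects with recurrent atrial tachyarrhythmia at which the study conclusion is changed". The safety text is parallel.

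**The tipping point is located by Z.** For effectiveness: "The tipping-point analysis will replace the missing values with effectiveness failures one at a time and the corresponding Z test statistic will be produced". The tipping point is reached when Z is no greater than the upper 2.5% normal quantile. For safety, missing values are replaced "with primary AE occurrence one at a time and the corresponding Z test statistic will be produced", and the tipping point is reached when Z is no smaller than the lower quantile. Neither section says which variance Z uses or whether it is continuity-corrected.

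**Populations.** For effectiveness, "All analyses will be performed in the PP and mITT populations". The safety analyses use the safety population.

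**The concern.** By the SAP's own definition, the tipping point is where the study conclusion flips. The exact interval sets that conclusion, so only the exact interval can say where it flips. A Z criterion answers a slightly different question.

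The mismatch shows inside a single section. The tipping analysis is to cover every possible outcome of the missing subjects, so its last row (all failures, or all events) is the worst-case data set. The worst case gets an exact interval and the tipping row gets a Z. Near the boundary, the two can report opposite verdicts on the same numbers.

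The open form of Z adds to this. The four usual forms do not agree with one another, so the choice would be left to the programmer in an unblinded single-arm study. The per-protocol table is robustness evidence for the primary effectiveness result, and the safety table is the same for the primary safety result, so both should follow the rule they are meant to test.

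**Working it through.** **Inputs.** Goals of 40% and 16%, two-sided 5% level, 330 evaluable and 367 enrolled subjects, anticipated rates of 50% and 8% (SAP sections 7 and 9). All counts of successes, events and missing subjects below are assumptions for illustration.

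**Formulas**, for x of n and goal p0, with p = x/n:
- Exact lower bound: Beta quantile 0.025 with parameters (x, n − x + 1). Exact upper bound: Beta quantile 0.975 with parameters (x + 1, n − x).
- Score Z = (p − p0) / √(p0(1 − p0)/n).
- Wald Z = (p − p0) / √(p(1 − p)/n).
- Corrected forms: reduce |p − p0| by 1/(2n) first.

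**1. The plan's own figures.** At n = 330 the exact rule needs 151 successes (lower bound 40.29%; 150 gives 39.99%). Power at a true 50% is 94.5%, consistent with the stated minimum of 90%. 330/0.90 = 366.7, hence 367. The plan gives no tipping-point figure to reproduce.

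**2. Effectiveness, one data set and two verdicts.** Take 155 successes in 330 observed and 12 missing. The worst case is 155/342 = 0.4532.
- Exact lower bound 39.96%: goal missed.
- Score Z = 0.05322/√(0.24/342) = 0.05322/0.02649 = 2.01: goal met.
- Wald Z = 0.05322/0.02692 = 1.98: goal met.
- Corrected score 1.954 and corrected Wald 1.923: goal missed, in agreement with the exact rule.

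Adding failures one at a time, the tipping point is 12 by the exact rule, 14 by score Z and 13 by Wald Z. These counts leave missing subjects who are not yet imputed out of the denominator. The SAP does not say whether that is intended, but the last row is the same either way.

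**3. Safety.** 46 events in 367 is 0.1253.
- Exact upper bound 16.36%: goal missed.
- Wald Z = −0.03466/0.01728 = −2.01: goal met.
- Score Z = −0.03466/0.01914 = −1.81: goal missed.

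**4. All sizes from 300 to 367 (68 sizes).** The table compares the success threshold or event limit under each Z form with the exact rule.

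| Form of Z | Effectiveness | Safety |
|---|---|---|
| Score | lenient by 1 at 39 | lenient by 1 at 10 |
| Wald | lenient by 1 at 20 | lenient by 1 at 36, by 2 at 32 |
| Corrected score | lenient by 1 at 7 | stricter by 1 at 21 |
| Corrected Wald | stricter by 1 at 13 | lenient by 1 at 67, by 2 at 1 |

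At all other sizes the form agrees with the exact rule.

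**5. At the planning values.** For 165/330 the tipping point is 36 by the exact rule, 37 by score and 36 by Wald. At n = 367 the score, Wald and corrected score forms all need 166 successes for effectiveness, the same as the exact rule.

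**6. How often the last row disagrees.** With 330 observed at a true 50%, this is the probability of the one discordant count:
- 10 missing: 2.1% (score or Wald; 154 successes).
- 20 missing: 3.3% (score; 158 successes), 0 (Wald).
- 37 missing: 0.

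For safety at a true 8%, 40 or 41 events in 330 (allowed by Wald, not by the exact rule) has probability 0.4%.

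**The case against.** The strongest reply is that nothing depends on it. Both primary decisions use the exact interval, and so does the worst case. If the worst-case exact bound clears the goal, no tipping point exists among the missing subjects, so the main robustness question already has an exact answer. Only the intermediate rows lack one. The table is there to help clinical judgment on whether a tipping point is implausible, and a shift of up to two subjects will rarely change that. The worked case was chosen at the boundary, where both corrected forms agree with the exact rule, and at full enrolment the score, Wald and corrected score forms agree for effectiveness.

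All of this stands, and it limits the size of the point. It does not make the text consistent: the criterion differs from the definition it serves, its form is open, and one section can contradict itself on the same data.

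A reader might go further and infer that the trial could be declared successful on a Z test. The documents do not support that, because Z appears only in the tipping analyses. Nor does Z always flatter the result, since its direction depends on the form.

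A reader might also object that mITT subjects with no RF delivered for reasons other than an investigational device deficiency are treated as missing, so that the best case scores them as successes, and might want them all scored as failures. The documents do not support that either. They do not list these subjects as failures. Protocol 4.1.1 says that a deficiency of a non-investigational device leading to use of a non-study catheter is not an acute failure. These subjects are followed for only 30 days, so treating them as missing, bounded by best and worst cases in a supportive analysis, is a defensible choice.

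**Conclusion.** The inconsistency is real and follows from the text alone. SAP 10.4.3.1 and 10.4.3.2 tie the tipping point to the study conclusion but find it with a different test, whose form is not fixed. Over sample sizes of 300 to 367 the consequence is at most one subject for effectiveness and two events for safety, and it shows only near the boundary. The primary decisions are unaffected. The illustrative verdicts rest on assumed counts; the comparison of rules over sample sizes does not. It is worth correcting because the remedy is nearly free and removes a choice that would otherwise be made after the data are seen.

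**What to change.** In SAP 10.4.3.1 and 10.4.3.2, replace the Z criterion with the exact two-sided 95% confidence interval at each tipping step: lower bound against 40% for effectiveness, upper bound against 16% for safety. Report the exact binomial p-value in the table, taken as twice the one-sided tail so that it matches the interval (for 155/342, twice P(X ≥ 155) at 40% is 0.052). In the same sentence, state whether missing subjects not yet imputed are left out of the denominator. The last row will then equal the worst case by construction.

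The cost is SAP wording and minor programming. The exact interval is already planned, and no data collection, sample size or primary analysis changes.
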